9.6 Safety Analyses

Safety will be assessed through the incidence of AEs and SAEs, which will be coded using MedDRA. The number and percentage of subjects reporting AEs and SAEs will be summarized at the MedDRA system organ class and preferred term level. Similar summaries will also be provided for AEs and SAEs related to the study device, as well as for AEs and SAEs related to the study procedure. Related events are those where the relationship is indicated as Unlikely, Possibly, Probably, or Causal. Summaries of all AEs and SAEs reported within the first 30 days after the initial ablation procedure will be generated. All reported adverse events will be listed.

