12.0 ADVERSE EVENTS

12.1 Definitions

Adverse Event

For this study, an adverse event is defined as any undesirable clinical occurrence in a patient. All AEs, whether attributable to the device/procedure or not, are to be recorded in the eCRF and reported to the Sponsor.

Expected Morbidity/Anticipated Adverse Events

An expected morbidity/procedural complication is defined as an AE that is known to be common or usual in nature, severity, or incidence during ablation of the lung.

Serious Adverse Event

It is the Investigator's responsibility to determine the "seriousness" of an AE using the protocol defined terms below. An SAE is an AE that results in one or more of the following for this study:

- Life-threatening: The patient was at imminent risk of dying at the time of the adverse event.
- Permanent Impairment: An AE that resulted in permanent impairment of a body function or permanent damage to a body structure.
- Necessitated Intervention: An AE that resulted in a condition that necessitated medical or surgical intervention to preclude permanent impairment of a body function or damage to a body structure.
- Required in-patient or prolonged hospitalization.
- A persistent or significant disability or incapacity.
- Resulted in death: An AE that resulted in the patient's death

Notes:

1. Progression of the disease under study should not be reported as an SAE.
2. "Death" should not be reported as an AE. The cause of death should be reported as an SAE. The only exception is "Sudden Death" when the cause is unknown.
3. Planned hospitalization for a pre-existing condition is not considered an SAE.
4. A procedure required by the protocol is not considered an SAE, unless the patient experiences a serious deterioration in health or hospitalization is prolonged.

The Sponsor will review all reported AEs and SAEs according to the current Safety Monitoring Plan.

Severity of Adverse Events

It is the Investigator's responsibility to assess the severity of an AE. A change in severity may constitute a new reportable AE.

The severity of each AE will be determined via the Common Terminology Criteria for Adverse Events (CTCAE) version 5.0. The CTCAE may be accessed here: https://ctep.cancer.gov/protocolDevelopment/electronic_applications/ctc.htm.

Also, the following guideline should be used to determine the severity of each AE:

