- **MILD:** Awareness of signs or symptoms, but does not interfere with the patient's usual activity, or is a transient event that resolves without treatment and with no sequelae.
- **MODERATE:** A sign or symptom, which interferes with the patient's usual activity.
- **SEVERE:** Incapacity with inability to do work or usual activities.

Relationship of Adverse Events

It is the Investigator's responsibility to assess the relationship between all AEs and the study procedure.

The following guidelines should be used in determining the relationship of an AE to a device, study procedure, or other causality:

Not related	Temporal sequence between device usage and the event is such that the relationship is unlikely.
Unlikely related	Temporal sequence between device usage and the event is such that the relationship is not unlikely or the subject's condition or concomitant therapy could have caused the AE.
Possibly related	Temporal sequence is relevant or the event abates upon device usage completion or the event cannot be reasonably explained by the patient's condition.
Probably related	Temporal sequence is relevant and the event abates upon product device usage or reappearance of the event on repeat device usage (re-challenge).
Causal relationship	Temporal sequence between device usage and the event is such that the relationship is unlikely.

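### The SAP counts 'Unlikely' events as related, the protocol's definition of that grade contradicts its label, and Tables 16-21 do not show such events separately

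*SAP*

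**What the plan says.** **The cut-off.** SAP 9.6 (Safety Analyses) states: "Related events are those where the relationship is indicated as Unlikely, Possibly, Probably, or Causal". The scale in Protocol 12.1 has five grades, so this takes in four and excludes only 'Not related'.

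**The grade at issue.** Protocol 12.1 (Relationship of Adverse Events) defines 'Unlikely related' by two alternatives joined by 'or'. The first is "Temporal sequence between device usage and the event is such that the relationship is not unlikely". The second is that "the subject's condition or concomitant therapy could have caused the AE".

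**The neighbouring grades.** 'Not related' is defined by timing alone: "Temporal sequence between device usage and the event is such that the relationship is unlikely". The same sentence is printed for 'Causal relationship'. 'Possibly related' is met by relevant timing, or by the event abating once device use ends, or if "the event cannot be reasonably explained by the patient's condition".

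**What the rule feeds.** The scale is for "determining the relationship of an AE to a device, study procedure, or other causality". Collection is broad: "All AEs, whether attributable to the device/procedure or not, are to be recorded in the eCRF and reported to the Sponsor". It runs from the start of ablation to the one-year visit (Protocol 12.2). The rule governs six SAP shells: device-related AEs and SAEs (Tables 16 and 17), procedure-related AEs and SAEs (18 and 19), and device-related AEs and SAEs within 30 days (20 and 21). All take the Table 14 format, which has one overall column of counts and percentages. Listing 29 gives every adverse event.

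**The concern.** Including 'Unlikely' would be an ordinary cautious cut-off if the grade had one meaning. Here it has two. An investigator who goes by the label uses it for an event thought probably unconnected with the device. One who goes by the definition uses it for an event with plausible timing, or with a plausible cause in the subject's own illness. The SAP then adds both kinds to the events graded Possibly, Probably or Causal.

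Device- and procedure-related events belong to the first-listed secondary endpoint (Protocol 6.2) and the first secondary objective. Protocol 7.3 defines medical inoperability by serious comorbidity, so adverse events with another possible cause are to be expected over a year. This is a first-experience study meant to inform a later one. If background illness is mixed into the related tables, a real device or procedure signal is harder to see. The SAP gives no reason for the cut-off, and no shell shows the result by grade.

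**Working it through.** The documents state no related-event rate, so there is no figure to reproduce. The check has a textual part and a scale part.

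**1. Where a comorbidity event can be graded.** Take an event that the subject's own illness could explain.

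- If the timing makes a link to the device improbable, it meets 'Not related'. It also meets 'Unlikely related' through the second alternative, because 'or' makes the other cause sufficient by itself.
- If the timing fits, it does not meet 'Not related'. It meets 'Unlikely related' through either alternative, and also 'Possibly related' if the timing is judged relevant.

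In the second case every grade that the event meets is counted as related under SAP 9.6, apart from the separate defect that 'Causal relationship' carries the 'Not related' sentence. Another plausible cause does not remove an event from the related set.

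**2. Whether the tables separate these events.** They do not. The shared format has one column. SAP 9.10 plans no sensitivity analysis and SAP 9.11 no subgroup analysis. Only the listing carries the grade.

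**3. Scale with 10 subjects.** SAP section 7 says enrollment stopped after 10 subjects received ablation. If u subjects enter a table only through 'Unlikely' events, the percentage rises by 100 × u/10 = 10u points. For u = 1 to 4 (an assumption; the documents give no value) that is 10 to 40 points. Moving from 1/10 to 5/10 changes the exact 95% interval from 0.3-44.5% to 18.7-81.3%. Those intervals are for orientation only, since the shells for Tables 16-21 show none.

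**4. Expected numbers under stated assumptions.** Let t be the probability that a subject has at least one event graded Possibly or stronger, and q the probability of at least one graded Unlikely. Take the two as independent. The expected number in a related table is 10t under the narrower rule and 10 × [1 − (1 − t)(1 − q)] under the SAP rule. For example, t = 0.10 and q = 0.3 give 10 × (1 − 0.90 × 0.70) = 3.7.

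| t | Narrower rule | SAP rule, q = 0.1 | q = 0.3 | q = 0.5 | q = 0.7 |
|---|---|---|---|---|---|
| 0.10 | 1.0 | 1.9 | 3.7 | 5.5 | 7.3 |
| 0.30 | 3.0 | 3.7 | 5.1 | 6.5 | 7.9 |

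Neither t nor q can be taken from the documents. The table shows how sensitive the count is to the cut-off; it does not predict a result.

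**The case against.** The strongest reply is that the SAP rule follows the protocol's text. An event whose relationship is described as not unlikely is reasonably counted as related, and in a first-experience study an inclusive rule errs toward reporting harm. The protocol does not say which grades count as related, so the SAP contradicts nothing. That stands, and it is why the broad count should stay. It does not answer the second alternative in the definition, or the label.

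Three stronger readings are tempting and are not supported.

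- A reader might infer that every event with a comorbid cause must be graded 'Unlikely'. The grades overlap, as step 1 shows, so the investigator may also choose 'Not related' or 'Possibly related'. A late event with implausible timing can properly be excluded.
- A reader might infer that the related tables cannot be interpreted at all. The SAP says openly which grades it counts. Protocol 12.2 has the relationship to device and to procedure recorded for each event, and Listing 29 allows a recount by hand for 10 subjects. Tables 14 and 15, which cover all AEs and SAEs, are unaffected.
- A reader might infer that the population is mostly severely comorbid. Operable patients who decline surgery may enter, and no proportion is given. ASA scores of 4 or more and expected survival under 6 months are excluded, and ECOG status must be 0-2.

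It is also fair to say that the eCRF wording and any completion guidance are not visible, so a split between investigators following the label and those following the definition is possible but not shown. No hypothesis test or stated decision depends on the related-event rate.

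**Conclusion.** The point holds as a matter of presentation and definition. The SAP cut-off, applied to a grade whose label and definition disagree, lets events with a plausible comorbid cause into six related-event tables that do not identify them. The bias is toward over-counting; nothing is concealed. Its size is 10 percentage points for each subject who enters only through an 'Unlikely' event, and the number of such subjects is unknown. The textual finding needs no assumption. The 10 to 40 point range and the expected counts rest entirely on assumed inputs. This is a low-cost improvement to make before the tables are produced, not a flaw that invalidates the safety analysis.

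**What to change.** 1. Keep the pre-specified broad count in Tables 16-21. Add two columns: subjects with at least one Possibly, Probably or Causal event, and subjects with Unlikely events only. Apply the split within each row, so that the two columns sum to the broad count. Use the device grade in Tables 16, 17, 20 and 21 and the procedure grade in Tables 18 and 19, in each case as originally recorded.
2. Footnote each table to say that the label and definition of 'Unlikely related' in Protocol 12.1 disagree.
3. Reconcile that wording together with the identical sentence given for 'Not related' and 'Causal relationship'. No cut-off on the scale can be fully judged until both are settled. New wording cannot change how events already recorded were graded, so the footnote is needed in any case.
4. Do not send queries on the 'Unlikely' records alone. In an open-label study with outcomes known, that invites regrading in one direction. If grades are to be confirmed, cover all categories and show the recorded grade beside the confirmed one.

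The cost is two extra columns in six shells and a footnote. SAP 9.1 already names an added footnote as a minor change. The new columns can be identified in the final output and documented in the study report, as that section requires for analyses that differ from the SAP. The one downside is that the narrower count may look more favourable to the device, so it should never appear without the broad one.

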9.7 Additional Endpoint Analyses

Counts and percentages will be provided for subject performance status as measured by the Eastern Cooperative Oncology Group (ECOG) classification at each visit. Summary statistics will be provided for the numeric pain rating scale measurement and hematology parameters at each visit. Pulmonary function tests will be summarized with summary statistics at each visit where they are measured and the change from the Screening visit measurement will also be summarized. Responses to each question of the EORTC QLQ-LC 13 will be summarized at each visit where the questionnaire was administered. Responses to the EORTC QLQ-C 30 will be listed.

Target lesion details including lesion type, lesion sub-type, size (largest and smallest diameter), location, distance from pleura, and shape will be summarized with statistics appropriate for categorical or continuous variables. Non-target lesion data will be listed. Selected information from the ablation procedure (duration of procedure, duration of ablation delivery, type of anesthesia, maximum power applied, and maximum temperature observed) will also be summarized with statistics appropriate for categorical or continuous variables.

Summary statistics will be presented for evaluations made by the independent reviewer for selected fields relating to ablation of the target lesion (largest diameter, smallest diameter, lesion location, distance from pleura, ablation margin, technical success, technique efficacy, and target lesion recurrence at any visit). All other target lesion data and all non-target lesion data from the independent reviewer will be listed.

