
Exploratory endpoints
	
 • Quality of life (QOL) questionnaires utilizing the European Organization for Research and Treatment of Cancer (EORTC) QLQ-C30 and the lung-specific QLQ-LC13 to be completed at Screening (Visit 1), pre-ablation (Visit 2A), on Day 1 just prior to discharge (Visit 2B), and at all follow-up visits (Visit 3 through Visit 5). • Numeric Pain Rating Scale, to be completed at Screening (Visit 1), pre-ablation (Visit 2A), on Day 1 just prior to discharge (Visit 2B) and at 30 days ± 7 days post-ablation (Visit 3).

Inclusion criteria
	
 1. Signed informed consent. 2. Patients ≥ 18 years old. 3. Performance status 0-2 (Eastern Cooperative Oncology Group classification [ECOG]). 4. Willing to fulfill all follow-up visit requirements. 5. Medically inoperable primary soft tissue lesion of the lung or patient election not to have surgery. (Medically inoperable is defined per the following indicators: post op predictive FEV1 < 40%; DLCO < 40%; hypoxemia or hypercapnia diabetes with end-organ damage; or severe cerebral, cardiovascular, peripheral vascular disease, or chronic heart disease).

	
6. A soft tissue lesion \leq 2 cm in the outer two-thirds of the lung and not closer than 1 cm to the pleura. Lesion size must be measured with at least 2-dimensional (2D) imaging. Only one lesion meeting the inclusion criteria may be treated during the day of ablation (Visit 2A). However, additional primary disease lesions may be present on the day of ablation.
 
(Outer two-thirds of the lung is defined as peripheral beyond the segmental airway, past the segmental bronchi, such that proximal endobronchial soft tissue lesions are avoided; soft tissue lesions should not be contiguous with the pleura).

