5.3 Exploratory Objectives

The exploratory objectives are the following:

1. To assess the quality of life post microwave ablation of the lung throughout the 1 year \pm 1 month follow-up period.
2. To assess the level of pain during the initial 30 days \pm 7 days post-ablation.

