8.2.2 Visit 2 – Ablation Procedure Through Discharge (Visit 2B)

[REDACTED]

[REDACTED]

On the day of ablation, cone beam CT scans will be done at the timepoints listed in the section below.

Visit 2A: Intraoperative (Ablation)

Data collected before and during the procedure:

- Administer antibiotics prior to the ablation procedure.
[REDACTED]
- Measure and record the size of the lesion to confirm inclusion criteria (lesion must be ≤ 2 cm).
- Prior to ablation, confirm that the patient still meets inclusion and exclusion criteria (tests not needed to be repeated).
- Collect height and body weight for BMI, and evaluate ECOG performance status (prior to ablation).
- Record all concomitant medications, including but not limited to chemotherapy, steroids, anti-inflammatories, NSAIDs, hormonal therapy, homeopathic /natural medications, nutritional supplements, and antibiotics. Do not record components of the anesthesia medications used for the ablation procedure.
- Record all concomitant procedures.
- QOL questionnaires EORTC QLQ-C30 and the lung-specific QLQ-LC13 (prior to ablation). The questionnaires may be administered over the phone, as needed.
- Numeric Pain Rating Scale (prior to ablation).

[REDACTED]

[REDACTED]

[REDACTED]

[REDACTED]

[REDACTED]

[REDACTED]

[REDACTED]

[REDACTED]

[REDACTED]

[REDACTED]

[REDACTED]

[REDACTED]

[REDACTED]

[REDACTED]

[REDACTED]

[REDACTED]

- User Experience Survey answered by the treating physician post-ablation (available as a separate document).
- Evaluate technical success, defined as ablation of the target lesion according to the protocol and covered completely, with an adequate margin, as defined by the performing physician (that is, the ablation zone completely overlaps or encompasses the target lesion plus an ablative margin).

[REDACTED]

- Radiation exposure from the CT scans.
- Record any AEs/SAEs that occur from the start of the ablation.

Visit 2B: Discharge

After the ablation procedure, the patient will be observed for up to 23 hours and afterwards discharged from the study site (except in cases where the Investigator deems it is necessary for the patient to remain hospitalized). During that 23-hour period, the following assessments will occur:

- Record all concomitant medications.
- Record all concomitant procedures.
- QOL questionnaires EORTC QLQ-C30 and the lung-specific QLQ-LC13. The questionnaires may be administered over the phone, as needed.
- Numeric Pain Rating Scale.

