10.9 Analyses to be Conducted

Analyses described below will be performed on the pooled set of 40 patients [REDACTED]

Disposition of Study Patients

Patient disposition will be summarized using counts and percentages. The number and percentage of patients completed and discontinued along with the specific reasons for discontinuation will be tabulated by treatment group and in total.

Demographic and Baseline Characteristics

Summary statistics will be provided for patient demographics and pre-operative ablation characteristics.

Primary and Secondary Endpoint Analyses

Device user experience feedback will be collected from the treating physician who will complete the User Experience Survey following each ablation procedure. The questionnaire will focus on procedure workflow and the user's assessment on ease/difficulty of using the device. Summary statistics will be provided for each question.

The number and percentage of patients achieving technical success will be summarized and a 95% confidence interval will be estimated. Technique efficacy, as well as primary and secondary efficacy rates and hospital readmission rates, will be summarized in a similar manner. Local soft tissue lesion recurrence rates will be estimated using the Kaplan-Meier method and 95% confidence intervals will be provided.

The number and percentage of patients experiencing AEs from the start of ablation (Visit 2A) to Visit 3 (the first post-ablation visit) will be summarized by MedDRA preferred term and system organ class. A similar summary will also be provided for device related and procedure related, and all SAEs. Ninety-five percent confidence intervals may be provided for pre-specified adverse events of interest [REDACTED]

[REDACTED]

[REDACTED]

[REDACTED]

[REDACTED]

[REDACTED]

[REDACTED]

[REDACTED]

[REDACTED]

[REDACTED]

[REDACTED]

Similar summaries will also be provided for the entire observation period from the ablation procedure date through 1 year of follow-up.

The EORTC QOL questionnaires and Numeric Pain Rating Scale scores will be summarized with methodology consistent to the recommendations of the specific survey. Additional endpoints will be summarized with descriptive statistics.

Plans for Interim Analysis

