9.1 General Conventions

Subject data will be summarized using listings and tables. All eCRF data will be listed per subject for all subjects. Descriptive statistical analyses will be provided for pre-specified study endpoints. Summaries for continuous variables will include number of observations (n), mean, standard deviation, median, minimum, and maximum. Summaries for categorical variables will include number and percentage.

Analyses will be conducted using SAS software version 9.4 or higher. During the course of analysis programming of tables that are mocked up in this SAP, minor modifications may become necessary. Examples of these minor modifications include, but are not limited to, re-wording of a footnote, addition of a footnote, re-labeling of a column, or addition or removal of a column from a listing. In cases where modifications to tables or listings are not related to a change in statistical analysis methodology or conclusions that could be made on the originally proposed methodology, then no amendment of the SAP is necessary. Any final analyses that differ from what has been specified in this document will be identified within the final statistical output and documented within the clinical study report.

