3	xx (xx.x%)
4	xx (xx.x%)
5 - Agree	xx (xx.x%)
Confidently Locate the Ablation Zone Created During Flex Ablation Procedure	
1 – Disagree	xx (xx.x%)
2	xx (xx.x%)
3	xx (xx.x%)
4	xx (xx.x%)
5 – Agree	xx (xx.x%)

Table 10
 Pulmonary Function Tests and Change From Screening Over Time
 Full Analysis Set

Parameter Statistic	Visit 1/ Screening	Visit 4/ Month 6	Change From Visit 1 to Visit 4	Visit 5/ Month 12	Change From Visit 1 to Visit 5
FeNO (ppb)					
n	xx	xx	xx	xx	xx
Mean	xx.x	xx.x	xx.x	xx.x	xx.x
Standard Deviation	x.xxx	x.xxx	x.xxx	x.xxx	x.xxx
Median	xx.x	xx.x	xx.x	xx.x	xx.x
Minimum, Maximum	xx.x, xx.x	xx.x, xx.x	xx.x, xx.x	xx.x, xx.x	xx.x, xx.x
DLCO (mL/min/mmHg)					
n	xx	xx	xx	xx	xx
Mean	xx.x	xx.x	xx.x	xx.x	xx.x
Standard Deviation	x.xxx	x.xxx	x.xxx	x.xxx	x.xxx
Median	xx.x	xx.x	xx.x	xx.x	xx.x
Minimum, Maximum	xx.x, xx.x	xx.x, xx.x	xx.x, xx.x	xx.x, xx.x	xx.x, xx.x
DLCO (%)					
SpO2 (%)					
FVC (mL)					
FVC (%)					
FEV1 (mL)					
FEV1 (% of predicted)					
FEV1/FVC (% of predicted)					
Plethysmographic TLC (mL)					
Plethysmographic TLC (% of predicted)					
Plethysmographic FRC (mL)					
Plethysmographic FRC (% of predicted)					
Gas Dilution TLC (mL)					
Gas Dilution TLC (% of predicted)					
Gas Dilution FRC (mL)					
Gas Dilution FRC (% of predicted)					

<<< Programming note: The number of observed responses at each time point are summarized. No imputation will be performed for subjects not responding at a given visit. >>>

Table 11
 Hematology Tests Over Time
 Full Analysis Set

Parameter Statistic	Visit 1/ Screening	Visit 3/ Day 30	Visit 4/ Month 6	Visit 5/ Month 12
RBC (M/uL)				
n	xx	xx	xx	xx
Mean	xx.x	xx.x	xx.x	xx.x
Standard Deviation	x.xxx	x.xxx	x.xxx	x.xxx
Median	xx.x	xx.x	xx.x	xx.x
Minimum, Maximum	xx.x, xx.x	xx.x, xx.x	xx.x, xx.x	xx.x, xx.x
WBC (K/uL)				
n	xx	xx	xx	xx
Mean	xx.x	xx.x	xx.x	xx.x
Standard Deviation	x.xxx	x.xxx	x.xxx	x.xxx
Median	xx.x	xx.x	xx.x	xx.x
Minimum, Maximum	xx.x, xx.x	xx.x, xx.x	xx.x, xx.x	xx.x, xx.x
Neutrophils (%)				
Lymphocytes (%)				
Monocytes (%)				
Eosinophils (%)				
Basophils (%)				
Hemoglobin (g/dL)				
Hematocrit (%)				
Mean Corpuscular Volume (fL)				
Platelet Count (K/uL)				
PTA (%)				
APTT (seconds)				
PT (seconds)				
INR (ratio)				

<<< Programming note: The number of observed responses at each time point are summarized. No imputation will be performed for subjects not responding at a given visit. >>>

Table 12
 Numeric Pain Rating Scale Over Time
 Full Analysis Set

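### Pain is summarised visit by visit, with no within-subject change from the pre-ablation score that the study collects

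*SAP*

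**What the plan says.** The protocol's second exploratory objective (section 5.3) is "To assess the level of pain during the initial 30 days" after ablation, with a window of 7 days either side of day 30. The Synopsis and the Schedule of Assessments place the pain scale at Screening, at Visit 2A, at Visit 2B before discharge, and at Visit 3. Protocol section 8.2.2 and the asterisk in the schedule make clear that the Visit 2A score is taken before ablation.

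On analysis, protocol section 10.9 says only that "Numeric Pain Rating Scale scores will be summarized with methodology consistent to the recommendations of the specific survey"; it names no change score. SAP section 9.7 says "Summary statistics will be provided for the numeric pain rating scale measurement and hematology parameters at each visit". Under SAP section 9.1, "Summaries for continuous variables will include number of observations (n), mean, standard deviation, median, minimum, and maximum". The shell for Table 12, titled "Numeric Pain Rating Scale Over Time", has four visit columns, each with its own n, and no change column.

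For pulmonary function tests, SAP section 9.7 adds that "the change from the Screening visit measurement will also be summarized", and Table 10 has the columns for it. SAP section 9.9 rules out imputation. Individual pain scores appear in Listing 12.

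**The concern.** A pain level on Day 1 or at day 30 is hard to read without knowing where each subject started. The study has that starting value for the day of ablation, but no planned table uses it within subject. If two subjects simply exchanged scores between Visit 2A and Visit 3, one worsening and one improving, Table 12 would look the same as if neither had changed. Pain is also among the adverse events of interest listed in SAP section 7, so how much it moves after ablation matters for safety as well as for the exploratory objective.

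A reader of Table 12 will naturally subtract one visit mean from another. That difference has no interval attached. If any subject lacks a post-ablation score, the two means also rest on different sets of subjects.

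**Working it through.** The documents give no effect size, SD or precision target for pain, so there is no figure of the plan's to reproduce. Three checks follow.

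**Inputs from the documents:** 10 subjects ablated (SAP section 7); scale from 0 to 10 (Table 12 footnote); observed data only (SAP section 9.9). **Assumed, not in the documents:** correlation r between two visits, from 0 to 0.7; equal SD at both visits; SD = 2 points where results are given in points.

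**1. Can the spread of change be recovered from Table 12?**

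SD of change = SD × √(2(1 − r)). Relative to the single-visit SD this is 1.41 at r = 0, 1.18 at r = 0.3, 1.00 at r = 0.5 and 0.77 at r = 0.7. By-visit SDs carry no information on r, so the answer is no, even with complete data.

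**2. When do the visit means mislead?**

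Let N = 10 subjects have a Visit 2A score and let k of them lack the later score. Write B for the Visit 2A mean.

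- Mean paired change = later mean − B(observed later)
- Difference of visit means = later mean − B(all 10)
- Gap between the two = B(all 10) − B(observed later) = (k/N) × [B(missing later) − B(observed later)]

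Results:

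- k = 0: gap 0. With complete data the difference of visit means equals the mean paired change exactly.
- k = 1: (1/10) × 3 = 0.3 points if the missing subject's baseline differs from the others' mean by 3 points; (1/10) × 5 = 0.5 if by 5; at most (1/10) × 10 = 1.0.
- k = 2: (2/10) × 3 = 0.6; (2/10) × 5 = 1.0; at most 2.0.

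**3. What would a paired interval gain with 10 complete pairs?**

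- Paired half-width = t(0.975, 9) × SD × √(2(1 − r)) / √10, with t = 2.262
- Half-width treating the visits as independent = t(0.975, 18) × SD × √(2/10), with t = 2.101
- Ratio = (2.262 / 2.101) × √(1 − r) = 1.077 × √(1 − r)

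At SD = 2 the independent half-width is 2.101 × 2 × 0.447 = 1.88 points.

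| r (assumed) | √(1 − r) | Width ratio | Paired half-width, 10 pairs | Paired half-width, 9 pairs |
|---|---|---|---|---|
| 0 | 1.000 | 1.08 (8% wider) | 2.02 | 2.17 |
| 0.3 | 0.837 | 0.90 (10% narrower) | 1.69 | 1.82 |
| 0.5 | 0.707 | 0.76 (24% narrower) | 1.43 | 1.54 |
| 0.7 | 0.548 | 0.59 (41% narrower) | 1.11 | 1.19 |

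The paired interval is the narrower one once r exceeds 1 − (2.101/2.262)² = 0.14.

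**The case against.** The strongest reply is that the plan answers the question it set. The objective concerns the level of pain, by-visit summaries report level, and neither document promises a change analysis for pain. This stands: a reader might infer that the SAP contradicts its own objective, and it does not.

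The contrast with pulmonary function can also be pressed too far. ECOG status, hematology and the QLQ-LC13 are likewise summarised by visit without change, so pulmonary function is the exception and pain has not been singled out. The SAP openly cut back analyses after enrolment stopped at 10, tests no hypotheses and plans no comparison between visits. Choosing a plain by-visit table for an exploratory measure is defensible.

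Table 12 also gives more than means, and with 10 subjects anyone can work out individual changes from Listing 12. That is true, so no information is lost. It does not replace a prespecified summary, though, because each reader would have to choose the baseline (Screening or Visit 2A) and the handling of incomplete pairs for themselves.

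**Conclusion.** The point holds as a gap in a descriptive exploratory analysis. No primary or secondary endpoint is affected and no conclusion is overturned. What is missing is a summary of within-subject change from the Visit 2A score; its SD and interval cannot be obtained from Table 12 as laid out.

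Three stronger readings are tempting, and the documents do not support them.

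- **That the visit columns do compare different subjects.** All columns draw on the same Full Analysis Set of 10, and pain collection ends at Visit 3. The sets differ only if a score is missing. The SAP reports one death but not its timing relative to Visit 3. The discrepancy of 0.3 points, or at most 1.0, is therefore conditional on one subject having a baseline score but no later one.
- **That paired change would cure dropout.** It puts the same subjects on both sides of the comparison, but a subject without a later score is still left out. Nothing in the documents shows that subjects with poor outcomes were lost before Visit 3.
- **That the interval would narrow by 29% to 45%.** Those are the reductions in standard error, 1 − 0.707 and 1 − 0.548. With 10 pairs the smaller degrees of freedom bring the narrowing in interval width to about 24% to 41%.

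The 24% to 41% rests on assumed correlations of 0.5 to 0.7, equal SDs and 10 complete pairs. The comparator, an interval treating visits as independent, is what a reader might construct from Table 12; the SAP does not plan one.

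**What to change.** Add two columns to Table 12, change from Visit 2A to Visit 2B and change from Visit 2A to Visit 3, among subjects with both scores. Give the paired n, mean, SD, median, minimum, maximum and a 95% confidence interval for the mean change. Name Visit 2A as the baseline in SAP section 9.7, and footnote that subjects without both scores are excluded and that the paired summary does not correct for selective dropout. Keep the by-visit columns, since they answer the stated objective.

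The cost is two columns and one sentence. The data are already collected and listed, Table 10 supplies the layout, and SAP section 5 already names 95% confidence intervals as the form of estimation.
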